Subjects will receive sufficient study drug/placebo supply to cover the period up to the next scheduled visit at Visit 5 and/or through Visit 7 as needed. We will instruct subjects to return all of the study drug packaging, including unused study drug and empty packaging at each study visit and/or at the time of discontinuation from treatment.

Study staff will review medication administration and use of the drug diary card with all subjects. Subjects will be asked to record the time they take the drug each day and any symptoms with severity rating and/or health events during the dosing period.

The study staff and/or CTRC RN will review biopsy site care with subjects and if indicated, remind subjects to resume their normal anti-coagulation/anti-platelet/anti-diabetic medications.

The subject will receive payment for visits 1-4 and can then be discharged.

Drug Dosing Period and Outpatient Monitoring

Subjects will then complete no less than 28 (-3) days on drug. Subjects will continue on drug/placebo through the post testing period; the duration will vary with the visit windows and if subjects are doing both 6A and 6B. During the 28-day period, subjects will be called on a weekly basis by study staff, beginning on the visit 4 day plus 7 days \pm 2 days, and continuing approximately weekly thereafter. Study staff will query subjects on any symptoms, home BP readings if applicable, health care, including medication changes, or adverse events, and compliance with study drug/placebo regimen. Any AEs or medical issues of concern will be promptly communicated to the PI or covering study physician by email or phone depending on urgency; and AEs will be documented in the study log which is reviewed with PI at least bi-

weekly. Subjects will be again reminded to communicate any medication changes prescribed by their health care team to study staff as soon as possible, not to wait for the weekly call. (Serious adverse events will be reported as described in Section 6.4.5.) Management of hypotension or methemoglobinemia related symptomatology will be as described in 2.3.3 Dose Selection, subsection Dose Reduction.

Post Assessments (continuing on NO₂/placebo tid)

Visit 5

This visit will be scheduled 28 ±3 days from Visit 4, take place in the UPMC Montefiore EMRC and/or Pepper SMART Center and include all of the Functional testing described in Visit 2.

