	Visit 3B (5 days ±2 days from V3A)	Symptom limited iCPET with associated exercise echocardiography
	Visit 4 (10 days ±4 days from V3A or 5 days ±2 days from V3B)	Research bloods**; Skeletal muscle biopsy; Administration of first dose of NO ₂ ; PK assessment and BP assessment; Drug distribution
Drug dosing	Weekly phone calls	Phone call monitoring of drug tolerance, symptom assessment, medication compliance, adverse events.
Post-Assessment Series	Visit 5 (28 ±3 days from Visit 4)	Non-invasive functional assessment battery: Symptom-limited nCPET; Fatigability assessments (perceived [SS] and performance [6MWT]), NIRS during nCPET, SS, 6MWT, accelerometry during nCPET, SS, 6MWT and 1 week at home with diary; Hand grip, SPPB, Questionnaires; issue 3DFR
	Visit 6A (5 days ±2 days from V5)	³¹ P MRS protocol; review 3DFR and return ActiGraph 6A or 6B per dates; pre-cath bloodwork if applicable
	Visit 6B (5 days ±2 days from V6A)	Symptom limited iCPET with associated exercise echocardiography
	Visit 7 (10 days ±4 days from V6A or 5 days ±2 days from V6B)	Frailty assessment, Skeletal muscle biopsy; Research bloods‡; echo after meal

*Unless Hgb within normal limits recently prior to Visit 1 and deferred by physician; †deferred if recent per physician discretion;

**Platelets, nitrite/nitrates (time 0), + nitrites/nitrates (time 30 mins, 60 mins, and 120 mins); inflammatory peptides (IL-1, IL-6, IL-15, TNFα); adipokines (leptin, adiponectin); vitamin D, GFR, BNP or NT-pro BNP, TSH, HgA1C (unless recently measured)

‡Platelets, nitrite/nitrates; inflammatory peptides (IL-1, IL-6, IL-15, TNFα); adipokines (leptin, adiponectin); BNP, GFR, unless recently measured

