2.5.4 Safety Analysis

We will describe and descriptively compare proportions of those with clinical endpoints/adverse events such as hospitalizations, urgent clinic/ER visits, and death between the treatment groups, as using chi-square and Fisher's exact tests for dichotomous outcomes with such a small number of participants is unlikely to reliably demonstrate statistical significance.

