6.4.3 Parameters to be monitored

The following progress will be monitored throughout the course of the research to ensure the safety of subjects as well as the integrity and confidentiality of their data.

- An evaluation of the progress of the research study, including subject recruitment and retention, and an assessment of the timeliness and quality of the data.
- A review of collected data (including adverse events, unanticipated problems, and subject withdrawals) to determine whether there is a change to the anticipated

benefit-to-risk assessment of study participation and whether the study should continue as originally designed, should be changed, or should be terminated.

- An assessment of external factors or relevant information (e.g. pertinent scientific literature reports or therapeutic development, results of related studies) that may have an impact on the safety and study participants or the ethics of the research study.
- A review of study procedures designed to protect the privacy of the research subjects and the confidentiality of their research data.

The severity of adverse changes in physical signs or symptoms will be classified as follows:

- Grade 1 (Mild): asymptomatic or mild symptoms; clinical or diagnostic observation only; intervention not indicated.
- Grade 2 (Moderate): minimal, local or noninvasive intervention indicated; limiting age-appropriate ADL (Activities of Daily Living).
- Grade 3 (Severe): medically significant but not immediately life-threatening; hospitalization or prolongation of hospitalization indicated; disabling; limiting self-care ADL.
- Grade 4 (Life-threatening): consequences; urgent intervention indicated.
- Grade 5 (Death): event is a direct cause of death.

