6.4.5 Reportable Adverse Event

For this study, a serious adverse event is any untoward clinical event that is thought by [name], PI, to be study-related, and results in any of the following outcomes:

1. Death
2. A life threatening adverse event
3. Inpatient hospitalization or prolongation of an existing hospitalization

4. A persistent or significant incapacity or substantial disruption of the ability to conduct normal life functions
5. A congenital anomaly or birth defect
6. Important medical events (that may not result in death, be life threatening, or require hospitalization) may be considered serious when, based upon appropriate medical judgment, they may jeopardize the patient, or subject, and may require medical, or surgical intervention to prevent one of the serious outcomes listed above.

If clinically important and unexpected adverse experiences or clinically important study-related adverse experiences occur, they will be recorded on the adverse event case report form.

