The Investigator will retain the data for the entire period of this study and will retain the specified records and reports for up to two years after the marketing application is approved for the investigational drug; or, if a marketing application is not submitted or approved for the investigational drug, until two years after investigations under the IND have been discontinued and the FDA so notified. The Investigator may continue to use and disclose subjects' de-identified information for the purpose of this study for a minimum of seven years after final reporting or publication of the study. If the subject and/or legal representative decide to withdraw or be withdrawn from study participation, they may request that the study data and samples be destroyed. Subject names or other directly identifiable information will not appear on any reports, publications, or other disclosures of clinical study outcomes.

Source data to be included in the clinical study data, either on the original form or recorded by staff include:

- a. Information taken from or copies of electronic medical records to confirm inclusion/exclusion criteria
- b. Echocardiogram testing and interpretation
- c. All progress notes
- d. Communications from referring physicians
- e. De-identified emails communicating subject clinical information to PI or study physician
- f. Assessments of vitals, body weight at all visits
- g. Data generated from the nCPET, iCPET, MRS and all functional assessments,
- h. Questionnaires completed by subjects
- i. CTSC records of patient visits
- j. Analyses of screening and outcome assessments of blood and muscle tissue from internal and external investigator lab analyses
- k. Data collected from subjects' drug and diary cards

Missing data points that are *anticipated* will be documented in the progress notes and evaluated with HRPO input regarding the need for an Exception Report, i.e., unanticipated absence of staff or investigator to perform test, unanticipated absence of subject. *Unintentional* missing data due to subject inability will be noted. These will be reported to the PI for evaluation and corrective action plan implemented as needed.

All staff performing assessments that are witness to data collection which may be spurious are advised to communicate to the PI. As most of the measurements are objective, this is not anticipated to be an issue.

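### The adverse event form need not hold mild events or important events judged expected and unrelated, and the safety analysis does not say whether it uses that form

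*Combined protocol and SAP*

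**What the plan says.** Section 6.4.5 gives the recording rule. If "clinically important and unexpected adverse experiences or clinically important study-related adverse experiences occur, they will be recorded on the adverse event case report form". Clinical importance is not defined. Reporting timelines to the review board and the FDA are handled separately, in 6.4.6.

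Section 2.5.4 plans a descriptive comparison of "proportions of those with clinical endpoints/adverse events such as hospitalizations, urgent clinic/ER visits, and death between the treatment groups". It does not say which record supplies the events.

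Other sections describe wider capture:

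- Section 6.4.3 grades severity from the bottom of the scale: "Grade 1 (Mild): asymptomatic or mild symptoms; clinical or diagnostic observation only; intervention not indicated".
- Section 2.2 says of events raised in the weekly calls that "AEs will be documented in the study log which is reviewed with PI". The visit table describes those calls as "Phone call monitoring of drug tolerance, symptom assessment, medication compliance, adverse events".
- Section 2.2 also has subjects enter on a diary card "any symptoms with severity rating and/or health events during the dosing period".
- Section 6.5.1 includes data from the "drug and diary cards" among the source data for the study.
- Sections 6.4.1 and 6.4.4 promise the Safety Officer monthly reports of all adverse events, and 6.4.2 has staff pass all of them to a physician investigator or the PI.

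**The concern.** The protocol describes at least three adverse event records with different contents: a form with a condition for entry, and a log and a diary without one. The analysis plan chooses none of them. If the form is used, two judgements are made before the arms are compared: whether an event matters, and whether the study caused it.

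The second judgement is the more troublesome. In a randomised, blinded trial, the difference in event rates between arms is the evidence on whether a symptom is due to the drug. If judged relatedness helps decide which events are counted, the comparison partly reflects that judgement.

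The results are meant to inform a larger trial, and section 2.3.3 reports mild, transient symptoms and a vasoactive response in the heart failure subjects of the ongoing pilot. An incomplete table of events by arm would be a poor basis for planning.

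**Working it through.** The plan gives no event rate or safety calculation to reproduce, so the check is one of logic and cross-reading.

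**Step 1. What 6.4.5 requires.** The rule is: (important and unexpected) or (important and study-related).

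| Clinically important | Unexpected | Study-related | Entry on form required |
|---|---|---|---|
| Yes | Yes | Yes | Yes |
| Yes | Yes | No | Yes |
| Yes | No | Yes | Yes |
| Yes | No | No | No |
| No | Either | Either | No |

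Two groups need not be on the form: everything judged not clinically important, and important events judged both expected and unrelated.

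**Step 2. Against the severity scale.** Grade 1 in 6.4.3 covers asymptomatic or mild findings that need no intervention. Most of these would fail a test of clinical importance, so the form need not hold most of the lowest grade that the protocol defines.

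**Step 3. Against the analysis.** Section 2.5.4 names hospital admissions and urgent visits as events to compare. In HFpEF patients aged 70 or over, an admission could be judged both expected and unrelated. It then falls in the fourth row. The serious-event definition in 6.4.5 does not bring it back, because that definition also requires the PI to think the event study-related. The form can therefore lack events that the safety analysis names.

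**Step 4. Against the other records.** The log, the diary and the reports to the Safety Officer carry no such condition. No text says that their contents are transferred to the adverse event form or used in 2.5.4. Section 2.5.6 has data recorded first on paper forms and entered on matching database screens, which makes the form a likely source but does not make it the only one. Section 6.5.1 names diary data and progress notes as source data; it does not name the log.

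**Step 5. Could the filter act differently by arm?** Sections 2.3.3 and 2.3.5 allow unblinding for high methemoglobin, for hypotension or light-headedness, and where the PI suspects that an event is drug-related. Once the arm is known, an important and expected symptom on placebo may be judged unrelated and left off, while the same symptom on nitrite is judged related and entered. This is a possible route; the documents do not show how often it would occur.

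**Step 6. Scale.** The planned size is 18, with 9 per arm. One affected subject missing from an arm changes that arm's proportion by 1/9 = 0.111, or about 11 percentage points.

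**The case against.** The strongest reply is that 6.4.5 says what must go on the form, not that nothing else may, and that its heading concerns reportable events. Mild events are also well captured elsewhere: baseline symptoms before dosing, diary severity ratings, weekly calls, and symptom, blood pressure and methemoglobin checks at Visits 5 to 7. Since 2.5.4 names no source, nothing shows that these data will be left out. This stands, and it limits the conclusion to what the comparison could omit. It does not remove the gap, because no text carries the information from the diary or log into the comparison.

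A reader might also infer that the form shuts out expected drug effects. The documents do not support that. The study-related branch has no unexpectedness condition, so hypotension listed as frequent in 6.1.1 must be entered when it is judged important and study-related. The pilot's dose reductions to prevent hypotension are, if anything, the kind of event most likely to meet the rule.

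Finally, section 2.5.2 will summarise post-randomisation adjustments and report reasons for withdrawal, which plausibly covers dose reductions, and methemoglobin is measured whether or not an event is recorded. That is fair. Listing both in 2.5.4 would mainly bring them together with the events by arm.

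**Conclusion.** The concern holds as a defect of recording and routing. The form rule in 6.4.5 conflicts with the Grade 1 category, with the wording on all adverse events and with the unfiltered log and diary. It can leave off admissions and urgent visits that 2.5.4 compares. If the comparison is built from the form, mild events and important events judged expected and unrelated could be missing, and judged relatedness would help decide the counts.

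The conclusion rests on two conditions: that staff apply 6.4.5 as the test for entry, and that the form is the source for 2.5.4. The documents suggest both and settle neither. They therefore do not support the stronger reading that known nitrite effects will be absent from the safety comparison. The number of events at risk cannot be estimated from the documents; only the weight of each subject, about 11 percentage points within an arm, can be stated.

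**What to change.** In 6.4.5, replace the recording sentence with one stating that every adverse event, whatever its grade, expectedness or judged relationship, is entered on the adverse event form with its 6.4.3 grade, start and stop dates, and relationship. Keep the present condition for expedited reporting only, and say so.

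In 2.5.4, name the adverse event form as the source and state that all recorded events are tabulated by arm, with dose reductions and methemoglobin above 5% listed. Events first noted in the diary, the calls or the log should be transferred to the form.

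The cost is one protocol sentence, a short addition to the analysis section and slightly more data entry. The diary, calls, log and visit checks already collect most of the information, and nothing in how subjects are managed changes.

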6.4.6. Adverse events reporting timeline

Life-threatening or fatal unexpected adverse events associated with the use of the study drug or procedures must be reported to the HRPO within 24 hours of discovery of the incident with subsequent follow-up submission of a detailed written report. The FDA must be notified by telephone or facsimile transmission of a human adverse event that is fatal or life-threatening no later than 7 calendar days after receiving the respective human adverse event information, followed by the subsequent submission of a written IND Safety Report.

Serious and unexpected adverse events associated with the use of the study drug or procedures must be reported to the HRPO with subsequent follow-up submission of a detailed written report in accordance with the respective policies and procedures of the HRPO. Written IND Safety Reports will be submitted to the FDA as soon as possible and, in no event, later than 15 calendar days following the investigator-sponsor's receipt of the respective adverse event information.

All reports noted in section 6.4.6 will also be provided to the NIA Program Officer and the protocol Safety Officer.

6.4.7. Withdrawal of Subjects and Stopping Criteria

Withdrawal of Subjects due to Adverse Events:

As described in Section 2.3.3. Dose Selection, sub-section Dose Reduction, we propose to discontinue participation for any subject who experiences any of the following:

- a. Continued MetHB level >5% or continued lightheadedness and/or dizziness after protocol described in Section 2.3.3 for dose reduction is followed.

Other symptoms
- b. The PI, via subject phone call monitoring, AE reports or at follow-up visits, will evaluate any other clinical presentation, sign or symptom in subjects which may warrant consideration of interim visit and dose reduction. The procedure described in Section 2.3.3. Dose Selection, sub-section Dose Reduction (regarding drug discontinuation and determination or need to withdraw the subject) will be followed.

Other Reasons for Withdrawal

Medication compliance

- c. In the event that the medication compliance rate is <80%, subjects will be re-educated on medication compliance. If medication compliance repeatedly falls outside of the

acceptable range, the study investigators will discuss subject eligibility for continued participation in the study.

- d. Participants who complete the first biopsy and then state (prior to being given drug) that they will not complete a second biopsy at Visit 7 will be withdrawn from the study. Alternatively, patients who refuse the 2nd biopsy after they have completed the 4 weeks of NO₂/placebo therapy will still complete the other post drug assessments. If other unique subject situations arise, they will be evaluated by the PI and a decision will be made with regard to completing the other post assessments or not (e.g., completion of 2 weeks on drug, and then refusal to complete biopsy.)
- e. The PI will evaluate any other clinical presentation, sign, symptom or behavior in subjects which may warrant consideration of withdrawal.

Discontinuation of the Clinical Trial

Stopping Rule:

Extensive published literature and considerable local experience at University of Pittsburgh indicates NO₂ is not inherently dangerous at the doses targeted in this trial. Certain side effects of NO₂ are idiosyncratic in older HFpEF patients and it is anticipated that there will be subjects who do not tolerate the treatment who may need to be withdrawn from the study as described for symptoms in 6.4.7. Nonetheless, if a subject enrolled in the study experiences a fatal event that is directly attributable to the NO₂, the overall study treatment will be discontinued.

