Subjects will be scheduled for an outpatient visit at the University of Pittsburgh CTSC in UPMC Montefiore within 10 days \pm 4 days from Visit 3A for subjects who did not complete iCPET or within 5 days \pm 2 days from Visit 3B for those who did complete iCPET.

Subjects will be asked to observe 8 hours fasting prior to arrival. Upon arrival subjects will be served a limited standardized breakfast.

This visit will last approximately 4-5 hours. To prevent acute effects of exercise on muscle mitochondrial function, this visit will occur no earlier than 2 days after Visit 3A/3B. Prior to the biopsy, study staff will call indicated subjects to hold their anti-platelet and anti-coagulation medications for 1-5 days (depending on the different medications and relative half-lives, as approved by their cardiologist). Subjects with diabetes who are on hypoglycemic medications will be advised if they need any adjustment to their usual regimen.

While the standardized breakfast is being prepared, subjects will undergo:

1. Interval history, measurement of BP and other vital signs (temperature, HR, body weight, RR, and SpO_2)

2. Staff will also confirm subject is fasting and that the anti-coagulation regimen was withheld as prescribed. Nursing will place an IV line.
3. A study physician will perform a brief physical exam.

4. Skeletal Muscle Biopsies

An important component of the protocol is the muscle biopsy. Subjects who refuse biopsy will not be enrolled. However, participants who complete the first biopsy and then state (prior to being given drug) that they will not complete a second biopsy at Visit 7 will be withdrawn from the study. Alternatively, patients who refuse the 2nd biopsy after they have completed the 4 weeks of NO₂/placebo therapy will still complete the other post drug assessments. If other unique subject situations arise, they will be evaluated by the PI and a decision will be made with regard to completing the other post assessments or not (e.g., completion of 2 weeks on drug, and then refusal to complete biopsy.)

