At this visit, methemoglobin will be assessed. If greater than 5%, the PI will be unblinded to drug or placebo assignment. If subjects are on nitrite, subjects will be asked to repeat drug dosing of 20 mg sodium nitrite with follow up methemoglobin and hemodynamic monitoring. A study physician or PI will evaluate data and make a determination regarding discharge on 20 mg tid. If discharged on 20 mg tid, subjects will be contacted via phone for the next 2 days for symptom re-assessment. If symptoms remain resolved, subjects will continue on 20 mg tid. If symptoms persist, subjects will be requested to come in for repeat methemoglobin testing after 3 days. If level persists above 5% on lower dose, participation in the study for the subject will be discontinued.

Hypotension and related symptoms.

In CTRC

If this occurs while in the CTRC, care will be administered, including fluids and monitoring, to ensure that the problem resolves and patient is stable. The physician investigator will factor relevant subject symptoms and hemodynamics and then decide whether unblinding is indicated and if it is appropriate for the subject to proceed with study participation prior to discharge from CTRC. This will include what dose is appropriate and drug dispensing. The same process will be applied to subjects who are initially initiated on 20 mg; however, in these subjects there is relatively greater consideration of withdrawal as no lower dosing options are available. The PI may indicate the need for a repeat pK with 20 mg dose in subjects who started on 40 mg study drug/placebo.

As outpatient:

If subjects experience lightheadedness or dizziness after visit 4 while they are on the study drug/placebo, we request that they call the study coordinator who will inventory their symptoms, compare to baseline levels (measured at pK), and discuss need for interim visit with study physician. If a visit is indicated, subjects will be asked to repeat drug dosing of 20 mg with follow up methemoglobin and BP pressure monitoring. A study physician will factor relevant subject symptoms and hemodynamics and will confirm a management plan including the:

- need for unblinding,
- possibility if subject was on sodium nitrite to lower dose to 20 mg tid or
- need to discontinue and drop from the trial.

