If subjects proceed on lower dose they will be reassessed via phone each day for the next 2 days thereafter to ensure that the patient is stable on the new dose. If stable, subjects will continue with the half dose. However if there are continued symptoms on lower doses, the physician investigator will reevaluate the patient's suitability for continued participation based on symptoms and/or hemodynamics.

If subjects who were initiated on the 20 mg dose at Visit 4 report symptoms as described above, they will be asked to complete an interim visit, methemoglobin and BP pressure assessment; the physician may have to withdraw the subject since a dose lower than 20 mg tid is not an option.

Other symptom

The PI, via subject phone call monitoring, AE reports or at follow-up visits, will evaluate any other clinical presentation, sign or symptom in subjects which may warrant consideration of dose reduction. The procedure described for high methemoglobin or hypotension will be followed.

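### Cheap improvement: participants who stop drug for intolerance before Visit 5 leave the study, and no visible rule collects their Aim 1 outcomes, so the intention-to-treat estimate falls back on imputation

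*Combined protocol and SAP*

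**What the plan says.** **Withdrawal.** Section 6.4.7, item a, covers a continued MetHb level above 5%, or continued lightheadedness or dizziness once the dose-reduction steps of 2.3.3 have been followed. For these it says "we propose to discontinue participation for any subject who experiences any of the following". Section 2.3.3 has the same sense for persistent MetHb above 5% on the lower dose ("participation in the study for the subject will be discontinued") and lists, among the outcomes of an interim visit for hypotensive symptoms, the "need to discontinue and drop from the trial". It is softer for symptoms that continue on the lower dose, where the physician re-evaluates "suitability for continued participation based on symptoms and/or hemodynamics", and for those who started on the lower strength: "the physician may have to withdraw the subject since a dose lower than 20 mg tid is not an option". The stopping-rule text in 6.4.7 expects some withdrawals for intolerance.

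**Outcome collection after stopping.** Item b of 6.4.7 refers to the 2.3.3 procedure "regarding drug discontinuation and determination or need to withdraw the subject", so the two ideas are named separately, but no assessments are attached to either. The drug distribution text in 2.2 also recognises discontinuation of treatment, but only for returning packaging. The one firm instruction to go on assessing covers refusal of the second biopsy after four weeks of treatment. For other unusual situations, "they will be evaluated by the PI and a decision will be made with regard to completing the other post assessments or not". Follow-up after an SAE withdrawal (6.4.2) concerns the event only.

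**Timing and analysis.** The functional battery is done at Visit 2 and repeated at Visit 5: "This visit will be scheduled 28 ±3 days from Visit 4". Section 2.5.3 declares Aim 1 intention-to-treat, with change in RPE as the primary outcome. Section 2.5.5 sends missing values to multiple imputation with five data sets in SAS MI and MIANALYZE. It does not name the imputation variables, say whether arm is included, or state a missingness assumption.

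**The concern.** Intention-to-treat needs the outcome of everyone randomised, including those who stopped drug. Under 2.5.3 the dependent variable is a change score at a single follow-up time, so the mixed model gains nothing from a participant without Visit 5, and only imputation can supply the value. The plan gives most weight to the size of the effect and will use its descriptive statistics to plan a larger trial. With early withdrawals, that size would depend partly on an imputation model that is not stated. The CONSORT diagram (2.5.2) and the missing-value summaries by arm (2.5.3) would show the loss without repairing it, and outcomes not collected cannot be recovered later. Section 6.1.1 lists hypotension as frequent in heart failure subjects on higher nitrite doses, so the loss could differ by arm.

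**Working it through.** **Inputs from the documents.** 9 nitrite + 9 placebo = 18. One post-baseline battery, at day 28 ±3. The plan gives no effect size, SD, power or withdrawal rate.

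**Assumptions.** k = nitrite participants withdrawn before Visit 5, of 9. D = effect on drug. g = effect in those who stop. Mean placebo change is 0, and no placebo outcomes are missing.

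**Formulas.**
- True intention-to-treat effect = [(9 − k)D + kg]/9
- Within-arm imputation = D
- Pooled imputation (arm ignored) = [(9 − k)D + k(9 − k)D/(18 − k)]/9
- Placebo-based imputation = (9 − k)D/9

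**Step 1: same observed data, different imputation.**
- k = 1: placebo-based 8/9 = 0.89D; pooled (8 + 8/17)/9 = 0.94D; within-arm 1.00D.
- k = 2: placebo-based 7/9 = 0.78D; pooled (7 + 2 × 7/16)/9 = 0.875D; within-arm 1.00D.

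**Step 2: error against the true effect, D = −2 RPE, k = 2.** The three estimates are −2.00, −1.75 and −1.56.

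| g (RPE) | True effect | Within-arm error | Pooled error | Placebo-based error |
|---|---|---|---|---|
| +1 | −1.33 | −0.67 | −0.42 | −0.22 |
| 0 | −1.56 | −0.44 | −0.19 | 0 |
| −1 | −1.78 | −0.22 | +0.03 | +0.22 |
| −2 | −2.00 | 0 | +0.25 | +0.44 |

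The sign can go either way. Placebo-based imputation is not a conservative bound: at g = +1 it gives −1.56 against a true −1.33.

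**Step 3: scale.** SE = SD × √(2/9), which is 0.71, 0.94 and 1.18 for an assumed SD of 1.5, 2 and 2.5. The largest error in the table, 0.67, lies below all three.

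**Step 4: does collecting the outcome help?** 4,000 simulated trials (9 v 9, baseline-adjusted model, five imputations, residual and baseline SD 2, D = −2, k = 2) gave these root mean squared errors:

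| g (RPE) | Outcomes collected | Within-arm | Pooled | Placebo-based |
|---|---|---|---|---|
| +1 | 0.98 | 1.27 | 1.03 | 0.89 |
| 0 | 0.98 | 1.16 | 0.96 | 0.85 |
| −1 | 0.97 | 1.09 | 0.93 | 0.88 |
| −2 | 0.97 | 1.06 | 0.97 | 0.94 |

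With outcomes collected, the mean estimates were −1.35, −1.57, −1.77 and −1.99, within 0.02 of the true effect. The simulation takes RPE to be measured without bias. Total error with collection is lower than with within-arm imputation, about equal to pooled, and higher than placebo-based.

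**Step 5: chance of any loss.** At assumed withdrawal rates of 5%, 10%, 20% and 30%, the chance of at least one among 9 is 1 − (1 − p)⁹ = 37%, 61%, 87% and 96%.

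**The case against.** The strongest reply is that this matters little in an 18-person pilot. The plan disclaims formal power, the error shown is smaller than sampling error, and placebo-based imputation has lower total error than collection in every simulated case. That stands, and it limits the point to a minor one.

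The frequency of withdrawal is also unsourced. The pilot reports that its heart failure subjects needed dose reductions; it reports no withdrawals. This trial has since adopted stratified starting doses, and methemoglobinemia is listed as rare. A reader might infer that substantial, nitrite-favouring bias is to be expected. The documents do not support that: neither the number of withdrawals nor the direction of bias is known. Full benefit kept off drug (g = D) is a weak case, since 2.3.3 reports plasma nitrite back at baseline about 3 to 6 hours after dosing in an early subject, although longer-lasting effects cannot be excluded.

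A reader might also infer that 2.3.3 and 6.4.7 contradict each other. Item a of 6.4.7 defers to 2.3.3 and applies only after its steps, so this is looser wording to be aligned, not a clear contradiction.

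The investigator may already decide to complete post assessments in unusual situations, and that wording is not confined to biopsy refusal. But it is discretion that may end in no assessment, not a collection rule.

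Finally, collection is not free of bias. Intolerance can lead to unblinding (2.3.3, 2.3.5), and RPE is self-rated. This stands and belongs in the fix.

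**Conclusion.** The point holds as a minor, inexpensive improvement. As visible, the plan ends participation for persistent intolerance and contains no rule to collect the Aim 1 outcomes afterwards. Part of section 2.3.3 was missing from the text reviewed, so a rule there cannot be excluded. Only withdrawals before Visit 5 lose treadmill RPE, the six-minute walk and non-invasive CPET. Later ones keep these, though one soon after Visit 5 could still lose the week of home actigraphy that serves the Aim 1 activity hypothesis.

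The size rests entirely on assumed k, D, g and SD. It would be wrong to conclude that collecting outcomes makes the estimate more precise, or that it removes all bias. It makes the estimate match its intention-to-treat label without relying on an imputation model for those participants, provided that RPE is reported without bias. The unstated imputation model is missing detail, secondary to the missing collection rule.

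**What to change.** 1. In 2.3.3 and 6.4.7, distinguish stopping study drug from withdrawing from the study. Leave the drug-stopping rules unchanged, and align the wording on continued symptoms in the two sections.
2. Ask every consenting randomised participant who stops drug, in either arm, to attend the scheduled Visit 5 for treadmill RPE, six-minute walk and non-invasive CPET, and to wear the ActiGraph for the following week. Unsafe or burdensome items can be skipped, as the Visit 5 text already allows.
3. Analyse these participants as randomised. Record whether each was on drug and whether unblinded at that visit.
4. In 2.5.5, keep multiple imputation for what is still missing, with treatment arm in the imputation model, and add a delta-shift sensitivity analysis in both directions (for example ±1 and ±2 RPE points). A shift of d on the imputed values moves the estimate by kd/9, so 1 point with k = 2 moves it by 0.22.

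**Cost.** Wording in three sections and a few attendances by participants who have stopped drug, at the $75 Visit 5 payment in 7.2; staff and testing costs are not given. The sample size stays at 18. Some participants will decline, so some imputation will remain, and RPE from unblinded participants may carry reporting bias.
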